3.2.1.3. Dose-Limiting Toxicities (DLT)

A DLT is defined as any TEAE not attributable to disease or disease-related processes or to concomitant medications or procedures that occurs during the DLT-evaluation period (Cycle 0, Day 1 to Cycle 1, Day 21 of Dose Escalation) and is Grade 3 or above, according to NCI-CTCAE version 5.0, with the exceptions as defined below.

For hematological toxicities, a DLT is defined as follows:

Hematologic Dose-Limiting Toxicities (DLT) NCI-CTCAE version 5.0		
Hematological toxicity	NCI-CTCAE Grade	CTCAE version 5.0 Definition
Neutrophil count decreased	4 (Lasting > 7 days or neutrophil count decreased that requires supportive therapy with myeloid growth factors)	< 500/mm ³ ; < 0.5 × 10 ⁹ /L
Febrile neutropenia	≥ 3	Grade 3: ANC < 1000/mm ³ with a single temperature of > 38.3°C or a sustained temperature of ≥ 38°C for more than one hour Grade 4: Life-threatening consequences; urgent intervention indicated
Anemia	4	Life-threatening consequences; urgent intervention indicated
Platelet count decreased	≥ 3 Lasting > 7 days or with clinically significant hemorrhage	Grade 3: < 50,000 – 25,000/mm ³ ; < 50.0 – 25.0 × 10 ⁹ /L Grade 4: < 25,000/mm ³ ; < 25.0 × 10 ⁹ /L
Lymphocyte count decreased	4 Lasting ≥ 14 days	< 200/mm ³ ; < 0.2 × 10 ⁹ /L
Any	5	Death

For hepatic organ toxicities, a DLT is defined as follows:

Hepatic Dose-Limiting Toxicities (DLT) NCI-CTCAE version 5.0		
Hepatic Organ Toxicity	NCI-CTCAE Grade	CTCAE version 5.0 Definition
Serum aspartate aminotransferase (AST) increase	4	> 20.0 × the upper limit normal (ULN) if baseline was normal; > 20.0 × baseline if baseline was abnormal
Serum alanine aminotransferase (ALT) increase	4	> 20.0 × ULN if baseline was normal; > 20.0 × baseline if baseline was abnormal
AST or ALT increased	3 Lasting >5 days	> 5.0 – 20.0 × ULN if baseline was normal; > 5.0 – 20.0 × baseline if baseline was abnormal
ALT or AST increased $\geq 3.0 \times$ ULN with simultaneous TBL increased $\geq 2.0 \times$ ULN	Not applicable	Not applicable
Any	5	Death

For pulmonary toxicities, a DLT is defined as any of the following:

Pulmonary Dose-Limiting Toxicities (DLT) NCI-CTCAE version 5.0		
Pulmonary Toxicity	NCI-CTCAE Grade	CTCAE version 5.0 Definition
Confirmed interstitial lung disease (ILD)	1	Asymptomatic; clinical or diagnostic observations only; intervention not indicated
	2	Symptomatic; medical intervention indicated; limiting instrumental activities of daily living (ADL)

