5.4. Dose Interruptions and Reductions

Following the DLT evaluation period (Section 3.2.1.3), the Investigator will evaluate which toxicities are attributed to the study drug and adjust the administration schedule of the drug. [Table 5.1](#) outlines schedule modifications for specific toxicities. Doses may also be interrupted for other toxicities per Investigator discretion, and supportive medication may be administered in accordance with local practice guidelines. All interruptions must be recorded on the drug administration electronic Case Report Form (eCRF).

In the event of a dose delay occurring prior to completion of a PK blood sampling in the study, Investigators should contact Sponsor medical monitor or designee for guidance regarding scheduling of these procedures.

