5.4.1. Dose Interruptions

During the DLT evaluation period, the administration of study drugs may be interrupted due to DLTs for up to 21 days according to the rules listed in [Table 5.1](#) below. When a DLT triggered interruption is required, both DS-1205c and gefitinib should be held. If a subject requires a dosing delay longer than 21 days, the subject will be withdrawn from the study.

For non-DLT TEAEs Grade 3 and above, study medications will be withheld for up to 3 weeks until improvement of the TEAE to Grade 2 or below. Study medications may be resumed after discussion and agreement between the Investigator and Sponsor. If the dosing interruption exceeds 21 days, the subject will be withdrawn from the study.

Table 5.1: Dose Interruption and Dose Resumption Criteria

	Worst toxicity NCI-CTCAE v5.0 Grade (unless otherwise specified) by Definition	Schedule modification for DS-1205c and gefitinib
General disorders and administration site conditions		
Fatigue/ Generalized muscle weakness	Grade 3 (Fatigue not relieved by rest, limiting self care ADL)	Delay study medications until resolved to \leq Grade 2, then: 
 • If resolved in \leq 7 days, resume study medications. • If resolved in $>$ 7 days and \leq 21 days, study medications may be resumed after discussion and agreement between the Investigator and Sponsor. • If not resolved in $>$ 21 days, discontinue subject from treatment.
Blood and lymphatic system disorders		
Neutrophil count decreased	Grade 3 ($< 1000-500/\text{mm}^3$; $< 1.0 - 0.5 \times 10^9/\text{L}$) Grade 4 ($< 500/\text{mm}^3$; $< 0.5 \times 10^9/\text{L}$)	Delay study medications until resolved to \leq Grade 2, then: 
 • If resolved in \leq 7 days, resume study medications. • If resolved in $>$ 7 days and \leq 21 days, study medications may be resumed after discussion and agreement between the Investigator and Sponsor. • If not resolved in $>$ 21 days, discontinue subject from treatment.
Febrile neutropenia	Grade 3 ($\text{ANC} < 1000/\text{mm}^3$, with a single temperature $> 38.3^\circ\text{C}$ or a sustained temperature of $\geq 38^\circ\text{C}$ for more than one hour) Grade 4 (Life-threatening consequences; urgent intervention indicated)	Delay study medications until neutrophil count decreased resolved to \leq Grade 2. Study medications may be resumed after discussion and agreement between the Investigator and Sponsor.

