Heart Failure	Grade 2 (Symptoms with moderate activity or exertion) Grade 3 (Symptoms at rest or with minimal activity or exertion; hospitalization; new onset of symptoms) Grade 4 (Life-threatening consequences; urgent intervention indicated [eg, continuous IV therapy or mechanical hemodynamic support])	Discontinue subject from study treatment. Cardiologist consult as necessary. Medical intervention as per institutional guidelines.
Ejection fraction (EF) decreased	Grade 3 (Resting EF 39 - 20%; \geq 20% drop from baseline)	Delay study medications until resolved to \leq Grade 2, then: 
 • If resolved in \leq 7 days, resume study medications. • If resolved in $>$ 7 days and \leq 21 days, study medications may be resumed after discussion and agreement between the Investigator and Sponsor. • If not resolved in $>$ 21 days, discontinue subject from treatment. Repeat LVEF assessment within 3 weeks. Cardiologist consult as necessary.
	Grade 4 (Resting EF $<$ 20 %)	Discontinue subject from study treatment. Cardiologist consult as necessary.

Table 5.1: Dose Interruption and Dose Resumption Criteria (Continued)

	Worst toxicity NCI-CTCAE v5.0 Grade (unless otherwise specified) by Definition	Schedule modification for DS-1205c and gefitinib
Electrocardiogram QT corrected interval prolonged	Grade 3 (Average QTc \geq 501 ms; QTc [ΔQTc] >60 ms change from-baseline)	Delay study medications until resolved to \leq Grade 1 (Average QTc 450 - 480 ms). Determine if another medication the subject was taking may be responsible and can be adjusted or if there are any changes in serum electrolytes that can be corrected. If mean QTcF prolongation is attributed to study treatment(s), the Investigator should have a discussion with the Sponsor before resuming study medications.
	Grade 4 (Torsade de pointes; polymorphic ventricular tachycardia; signs/symptoms of serious arrhythmia)	Discontinue subject from study treatment. Cardiologist consult as necessary.
Respiratory, thoracic and mediastinal disorders		

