9.3.2. Prolonged QTc Interval (\geq Grade 2)

Standard ECG parameters will be measured, including RR, PR, QT intervals, and QRS duration. Safety ECGs will be reviewed and interpreted on-site by the Investigator and evaluated by central reviewer. QTc prolongation more than Grade 2 (average QTc 481 - 500 ms) should be reported as a AESI. For more information regarding collection of ECGs, refer to Section 9.10.

If a subject experiences QTc prolongation of Grade 4 (torsades de pointes or polymorphic ventricular tachycardia or signs/symptoms of serious arrhythmia), then the subject should be discontinued from study treatment.

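### For Grade 3 QTc events that are not DLTs, Section 5.4.1 prints two restart limits, 500 ms in its general paragraph and 480 ms in Table 5.1, and no sentence expressly ranks them

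*Combined protocol and SAP*

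**What the plan says.** Section 5.4.1 has a general paragraph for non-DLT TEAEs of Grade 3 or higher: "study medications will be withheld for up to 3 weeks until improvement of the TEAE to Grade 2 or below". Restart then needs discussion and agreement between Investigator and Sponsor, and an interruption of more than 21 days means withdrawal. The paragraph has no exclusion for toxicities listed in Table 5.1.

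Table 5.1, in the same section, has its own row for Grade 3 QTc prolongation (average QTc of 501 ms or more, or a rise above 60 ms from baseline): "Delay study medications until resolved to \leq Grade 1 (Average QTc 450 - 480 ms". The row continues: "Determine if another medication the subject was taking may be responsible and can be adjusted". It brings in the Sponsor only conditionally: "If mean QTcF prolongation is attributed to study treatment(s), the Investigator should have a discussion with the Sponsor before resuming study medications".

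Three other places decide which events meet which rule:

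- Section 9.3.2 gives Grade 2 in milliseconds: "QTc prolongation more than Grade 2 (average QTc 481 - 500 ms) should be reported as a AESI".
- Section 3.2.1.3 limits a DLT to an event "that occurs during the DLT-evaluation period (Cycle 0, Day 1 to Cycle 1, Day 21 of Dose Escalation" and excludes events attributable to disease, concomitant medications or procedures.
- Section 5.4 says that after the DLT period Table 5.1 "outlines schedule modifications for specific toxicities". The DLT paragraph of Section 5.4.1 also sends DLT holds to the table.

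**The concern.** A Grade 3 QTc event after Cycle 1 Day 21 cannot be a DLT. Read literally, it falls under the general paragraph by that paragraph's own words and under the QTc row through Section 5.4. The same holds for an event inside the DLT period that is put down to disease, a concomitant medication or a procedure. One text then allows restart at up to 500 ms and the other only at 480 ms or less.

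This matters because the rule governs re-exposure to a drug that inhibits hERG (IC50 0.13 µM, Section 1.1.2.2) and has no human data (Section 1.1.3). The monkey ECG findings were clean and the protocol rates the clinical risk as low, but it commits to careful ECG monitoring and makes QTc prolongation an adverse event of special interest. With approximately 20 sites, similar events could be handled differently. Interruptions and restarts also feed the tolerability assessment, which is part of the primary objective.

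**Working it through.** The plan states no figure to reproduce. The check sets the two rules side by side and works out where they differ.

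**Which events meet both rules**

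| Grade 3 QTc event | General paragraph | Table 5.1 QTc row |
|---|---|---|
| In the DLT period, qualifies as a DLT | does not apply | applies |
| In the DLT period, attributed to disease, concomitant medication or procedure | applies | applies; the row itself considers another medication as the cause |
| After Cycle 1 Day 21 | applies on a literal reading | applies through Section 5.4 |

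QTc is not named in the DLT tables or among their exceptions, so its DLT status in the first row rests on the general Grade 3 or above definition.

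**How far apart the limits are**

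Inputs: Grade 1 ends at 480 ms (Table 5.1); Grade 2 is 481 to 500 ms (Section 9.3.2); a rise above 60 ms is Grade 3 (Table 5.1). I read the two Grade 3 criteria as alternatives, so a subject whose rise still exceeds 60 ms cannot restart under either rule. For a baseline of b ms the highest QTc at which dosing may restart is:

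- QTc row: T(b) = min(480, b + 60)
- General paragraph: P(b) = min(500, b + 60)

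| b (ms) | T(b) | P(b) | Difference (ms) |
|---|---|---|---|
| 400 | 460 | 460 | 0 |
| 410 | 470 | 470 | 0 |
| 420 | 480 | 480 | 0 |
| 430 | 480 | 490 | 10 |
| 440 | 480 | 500 | 20 |
| 450 | 480 | 500 | 20 |
| 470 | 480 | 500 | 20 |

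The last two rows are the screening limits for men and women in exclusion criterion 12, so baselines in the affected range are permitted. At b = 450 the rise remaining at restart is 480 − 450 = 30 ms under the row and 500 − 450 = 50 ms under the paragraph. At b = 470 it is 10 ms and 30 ms.

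Example: baseline 450 ms, event at 510 ms, now 490 ms. The rise is 490 − 450 = 40 ms, so the event is Grade 2. The paragraph permits restart with Sponsor agreement; the row keeps both drugs on hold.

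**Other differences between the two texts**

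- The paragraph asks for Sponsor agreement before every restart. The row asks for a Sponsor discussion only if the event is attributed to study treatment.
- For heart failure of Grade 2 to 4 the table says "Discontinue subject from study treatment. Cardiologist consult as necessary. Medical intervention as per institutional guidelines", whereas the paragraph, for non-DLT events of Grade 3 or higher, only withholds dosing. Grade 4 QTc prolongation shows the same contrast.
- The QTc row has no 21-day rule. For a non-DLT event the only explicit 21-day maximum is in the general paragraph.

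**The case against.** The strongest reply is that the specific rule beats the general one. Section 5.4 assigns specific toxicities after the DLT period to Table 5.1, the table covers resumption as well as interruption, and its QTc row has its own millisecond limit. The rows that require discontinuation support this, since a general paragraph can hardly be meant to turn mandatory discontinuation into a hold. This stands as the likelier intent, so a reader should not infer that the protocol gives no guidance on which limit governs. It remains an inference, and it cannot be applied by simply setting the paragraph aside, because the paragraph supplies the 21-day maximum that the QTc row lacks.

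A second reply is that Section 5.4.1 opens with the DLT evaluation period, so the paragraph may be meant for that period only. Events from Cycle 2 on would then follow the table alone. That is possible, but the paragraph does not say so, and in-period events attributed to other causes would still meet both rules. Those should be few as far as medication is concerned: QT-prolonging drugs are prohibited and need at least 10 days of washout.

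A third reply is that little follows in practice. Restart under the paragraph is permissive and needs Sponsor agreement, and a clause after Table 5.1 allows documented case-by-case exceptions. Restart at 490 ms could therefore be agreed under either text, and an unnoticed restart is unlikely. This stands, and it limits the weight of the point. But neither step tells the Sponsor which limit is the ordinary rule, or whether restart at 490 ms has to be recorded as an exception.

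**Conclusion.** The point holds for non-DLT Grade 3 QTc events. Followed as written, the general paragraph permits re-dosing, with Sponsor agreement, at 481 to 500 ms, a range in which the protocol's own QTc row keeps the hold. The gap is zero for baselines of 420 ms or less and reaches 20 ms at 440 ms and above. This rests on reading the two Grade 3 criteria as alternatives and, for events after Cycle 1 Day 21, on reading the paragraph literally. The documents give neither a baseline QTcF distribution nor an event rate, so how often it would matter is unknown.

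Three stronger conclusions might be drawn, and the documents do not support them:

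- That every Grade 3 QTc hold has two limits. DLT holds follow Table 5.1 alone.
- That a subject who stays at 481 to 500 ms beyond 21 days is withdrawn under the table. The QTc row has no such rule; withdrawal would come from the general paragraph's limit combined with the table's release grade.
- That dose escalation or a statistical result is affected. The model uses DLT outcomes from the DLT period (Sections 3.2.1.2 and 11.11.3), and no statistical figure changes.

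This is a wording defect in a cardiac-safety restart rule: small in scope, but worth correcting in a study with no prior human data.

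**What to change.** Add to the non-DLT paragraph of Section 5.4.1: *For toxicities listed in Table 5.1, the table's release and discontinuation criteria apply to DLT and non-DLT events alike where they are stricter than this paragraph; the 21-day maximum interruption applies to all toxicities.*

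The last clause is needed. A sentence that merely confined the paragraph to unlisted toxicities would remove the only explicit 21-day maximum for non-DLT QTc holds, and for febrile neutropenia, whose row also has none.

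Also state whether Sponsor agreement is required for every Grade 3 QTc restart or only for events attributed to study treatment. If the Sponsor's clinicians prefer Grade 2 as the QTc limit, change the row instead, so that one limit remains.

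The cost is one sentence and one clause, with no new assessments. The downside of keeping 480 ms is that some subjects with a baseline above 420 ms stay off drug longer, and a few may reach the 21-day limit.

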	3	Severe symptoms; limiting self care ADL; oxygen indicated
	4	Life-threatening respiratory compromise; urgent intervention indicated (eg., tracheotomy or intubation)
	5	Death
Any other pulmonary toxicity	≥ 3	Grade 3: Severe or medically significant but not immediately life-threatening; hospitalization or prolongation of

		existing hospitalization indicated; limiting self care ADL Grade 4: Life-threatening consequences; urgent intervention indicated Grade 5: Death
--	--	---

For non-hematological, non-hepatic, or non-pulmonary organ toxicities (ie, any other Grade ≥ 3 non-hematologic, non-hepatic, non-pulmonary toxicities including Grade 5 events), a DLT is defined as any of the following:

Dose-Limiting Toxicities (Non-Hematologic, Non-Hepatic, Non-Pulmonary Toxicities)		
DLT	NCI-CTCAE Grade	CTCAE version 5.0 Definition
Symptomatic heart failure	2	Symptoms with moderate activity or exertion
	3	Symptoms at rest or with minimal activity or exertion; hospitalization; new onset of symptoms
Left ventricular ejection fraction (LVEF)	3	Resting ejection fraction (EF) 39 – 20%; $\geq 20\%$ drop from baseline
Endocrine toxicities	≥ 3 Which do not resolve in ≤ 14 days	Grade 3: Severe or medically significant but not immediately life-threatening; hospitalization or prolongation of existing hospitalization indicated; limiting self care ADL Grade 4: Life-threatening consequences; urgent intervention indicated

The following TEAEs are considered DLTs
Thrombocytopenia requiring transfusion. Anemia requiring transfusion Inability to complete at least 75% of the prescribed doses (ie, at least 42 doses of DS-1205c and 16 doses of gefitinib) in the 7 days of Cycle 0 and the 21 days of Cycle 1 as a result of Grade ≥ 2 AE not attributed to disease.

The following TEAEs are NOT considered DLTs:

The following TEAEs are NOT considered Dose Limiting Toxicities		
TEAE	NCI-CTCAE Grade	CTCAE version 5.0 Definition
Fatigue	3 Lasting \leq 7 days	Fatigue not relieved by rest, limiting self care ADL
Nausea	3 That resolves to \leq grade 2 in 48 hours	Inadequate oral caloric or fluid intake; tube feeding, TPN, or hospitalization indicated
Vomiting	3 That resolves to \leq grade 2 in 48 hours	Tube feeding, TPN, or hospitalization indicated
Diarrhea	3 That resolves to \leq grade 2 in 48 hours	Increase of \geq 7 stools per day over baseline; hospitalization indicated; severe increase in ostomy output compared to baseline; limiting self care ADL

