Respiratory, thoracic and mediastinal disorders	Grade 2 (Symptomatic; medical intervention indicated; limiting instrumental ADL) Grade 3 (Severe symptoms; limiting self care ADL; oxygen indicated) Grade 4 (Life-threatening respiratory compromise; urgent intervention indicated [e.g., tracheotomy or intubation])	If new or worsening pulmonary symptoms (eg, dyspnea, cough, low-grade fever) or radiological abnormality suggestive of interstitial lung disease (ILD) is observed, an interruption in study treatment dosing is recommended, and the Sponsor should be informed . If a subject is suspected or diagnosed as having ILD, the Investigator should consult with a pulmonologist as needed, and the subject should be treated accordingly. The results of the full diagnostic workup (eg, high-resolution computed tomography (HRCT), blood and sputum culture, hematological parameters, arterial blood gas (ABG), pulmonary function testing, diffusing capacity of the lungs for carbon monoxide [DLCO]) should be recorded within the eCRF. It is strongly recommended to perform a full diagnostic workup, to exclude alternative causes such as lymphangitic carcinomatosis, infection, allergy, cardiogenic edema, or pulmonary hemorrhage Unscheduled imaging and laboratory results should be included in the eCRF.

Table 5.1: Dose Interruption and Dose Resumption Criteria (Continued)

	Worst toxicity NCI-CTCAE v5.0 Grade (unless otherwise specified) by Definition	Schedule modification for DS-1205c and gefitinib
		If a non-inflammatory cause is confirmed, this should be treated accordingly, and resumption of study drug may occur after discussion between the Investigator and Sponsor. Study treatment will be permanently discontinued upon confirmation of drug-induced ILD or drug-induced pneumonitis.
Endocrine disorders	Grade 3 (Severe or medically significant but not immediately life-threatening; hospitalization or prolongation of existing hospitalization indicated; limiting self care ADL)	Delay dose until resolved to \leq Grade 2, then: 
 • If resolved in \leq 14 days, resume study medications. • If resolved in $>$ 14 days and \leq 21 days, study treatment may be resumed after discussion and agreement between the Investigator and Sponsor. • If not resolved in $>$ 21 days, discontinue subject from treatment.
	Grade 4 (Life-threatening consequences; urgent intervention indicated)	Discontinue subject from study treatment.

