9.3.3. Interstitial Lung Disease

Lung disorders, including interstitial lung disease (ILD), are acknowledged in the current reference safety information for gefitinib (see current prescribing information). If a subject is suspected or diagnosed as having ILD, the Investigator should consult with a

pulmonologist as needed, and the subject will be treated appropriately. The study treatments will be interrupted until drug induced pulmonary toxicity can be ruled out. Study treatments will be permanently discontinued upon confirmation of drug-induced ILD or pneumonitis. It is strongly recommended to perform a full diagnostic workup, to exclude alternative causes such as lymphangitic carcinomatosis, infection, allergy, cardiogenic edema, or pulmonary hemorrhage. See Section 9.12 for details regarding pulmonary assessments.

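### Section 9.3.3 and Table 5.1 give inconsistent hold and restart instructions for suspected ILD, and in a limited set of Grade 2 cases the restart reading decides DLT status

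*Combined protocol and SAP*

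**What the plan says.** **Hold.** Section 9.3.3, for a subject suspected or diagnosed as having ILD: "The study treatments will be interrupted until drug induced pulmonary toxicity can be ruled out". Table 5.1, respiratory row, for new or worsening pulmonary symptoms or a radiological abnormality suggestive of ILD: "an interruption in study treatment dosing is recommended, and the Sponsor should be informed".

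**Restart.** Under Section 9.3.3 the hold ends when drug-induced toxicity is ruled out. Table 5.1 states one route: "If a non-inflammatory cause is confirmed, this should be treated accordingly, and resumption of study drug may occur after discussion between the Investigator and Sponsor". The same row asks for a full work-up "to exclude alternative causes such as lymphangitic carcinomatosis, infection, allergy, cardiogenic edema, or pulmonary hemorrhage".

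**Permanent stop.** The two passages agree. Table 5.1 has "Study treatment will be permanently discontinued upon confirmation of drug-induced ILD or drug-induced pneumonitis", and Section 9.3.3 says the same in substance.

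**Exceptions.** The note under Table 5.1 allows documented case-by-case exceptions agreed between Investigator and Sponsor. It gives no criterion.

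**Link to DLT status.** Among the events that Section 3.2.1.3 counts as DLTs is "Inability to complete at least 75% of the prescribed doses (ie, at least 42 doses of DS-1205c and 16 doses of gefitinib" over Cycle 0 and Cycle 1, when the cause is a Grade 2 or higher AE not attributed to disease. In the pulmonary DLT table, confirmed ILD of any grade is a DLT, and so is any other pulmonary toxicity of Grade 3 or higher.

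**The concern.** ILD is an adverse event of special interest here, and two sections direct its management differently.

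On the hold, a subject whose scan suggests ILD could stay on both drugs during the work-up under Table 5.1, but not under Section 9.3.3.

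On restart, a confirmed infectious or allergic cause ends the hold under Section 9.3.3, because drug-induced toxicity has been ruled out. In Table 5.1 that subject falls between two conditions: the cause is not non-inflammatory, and it is not drug-induced ILD or pneumonitis. The row is silent.

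The first stake is subject safety and consistent handling across sites. The second is the primary endpoint. A subject who is not restarted loses doses, and enough lost doses through a Grade 2 event is itself a DLT. With a minimum of three DLT-evaluable subjects per dose level (Section 11.9), one reclassified subject can alter what the escalation model recommends.

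**Working it through.** **Inputs.** DLT window: 7 days of Cycle 0 plus 21 days of Cycle 1 (Section 3.2.1.2). DS-1205c is given twice daily throughout and gefitinib once daily from Cycle 1 Day 1 (Section 3.2.1). Dose thresholds: Section 3.2.1.3. Model, prior and escalation rule: Sections 11.11.1 to 11.11.3.

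**Step 1: reproduce the plan's thresholds.** DS-1205c: 28 × 2 = 56 doses, and 0.75 × 56 = 42. Gefitinib: 21 doses, and 0.75 × 21 = 15.75, rounded up to 16. Both match the plan.

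**Step 2: set the passages side by side.**

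| Situation | Section 9.3.3 | Table 5.1 |
|---|---|---|
| Imaging suggestive of ILD, work-up pending | Hold required | Hold recommended |
| Non-inflammatory cause confirmed | Hold ends if drug-induced toxicity is ruled out | May resume after discussion |
| Infection or allergy confirmed, drug-induced toxicity ruled out | Hold ends | No instruction; exception clause only |
| Drug-induced ILD or pneumonitis confirmed | Permanent stop | Permanent stop |

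The first and third rows disagree. Elsewhere in Table 5.1, the row for raised transaminases with raised bilirubin ties resumption to drug-induced injury being ruled out. So the table itself uses a rule-out test in one place and a different test, confirmation of a non-inflammatory cause, in the respiratory row.

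**Step 3: doses under each restart reading.** Assume whole days missed, both drugs held together, no other missed doses, and Cycle 1 starting on study day 8.

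- Hold of h days wholly within Cycle 1: DS-1205c = 56 − 2h; gefitinib = 21 − h.
- Stop before the dose on study day s (s ≥ 8) with no restart: DS-1205c = 2(s − 1); gefitinib = s − 8.

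Example: Grade 2 pneumonia not attributed to disease, held from Cycle 1 Day 8 (study day 15).

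- Restart after 4 days: 56 − 8 = 48 and 21 − 4 = 17. Both thresholds are met, so there is no DLT.
- No restart: 2 × 14 = 28 and 15 − 8 = 7. Both thresholds are missed, so it is a DLT.

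**Step 4: where the two readings diverge.** Both thresholds are taken as having to be met.

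- A 5-day hold leaves 46 and 16 (no DLT). A 6-day hold leaves 44 and 15 (gefitinib short, so a DLT even with restart).
- A stop on study day 23 leaves 44 and 15 (DLT). A stop on study day 24 leaves 46 and 16 (no DLT even without restart).

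The split therefore needs a stop on or before study day 23 and a Section 9.3.3 hold of at most 5 days within Cycle 1.

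**Step 5: effect on the model.** logit π(d) = log α + β log(d/800), with the stated bivariate normal prior on (log α, log β): means −1.1493 and −0.5514, SDs 2.0739 and 1.5228, correlation −0.1943. The posterior was obtained from 2,000,000 prior draws weighted by the binomial likelihood, taking d as the single BID dose in mg (an assumption). Prior medians came out at 8.0% at 200 mg and 24.1% at 800 mg, against the plan's approximate 8% and 24.5%.

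After 0/3 at 200 mg, each cell gives P(DLT rate in target interval) / P(DLT rate > 0.33):

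| Dose | 400 mg: 0/3 | 400 mg: 1/3 |
|---|---|---|
| 200 mg | 0.044 / 0.006 | 0.236 / 0.078 |
| 400 mg | 0.083 / 0.016 | 0.336 / 0.169 |
| 600 mg | 0.133 / 0.049 | 0.344 / 0.293 |
| 800 mg | 0.180 / 0.127 | 0.320 / 0.385 |

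With 0/3, all doses satisfy the 0.25 limit and 800 mg has the highest target probability. With 1/3, 600 mg and 800 mg breach the limit and 400 mg is recommended.

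**The case against.** **The passages can be read together.** Table 5.1 does not say that other causes forbid resumption, and its only ban is for confirmed drug-induced ILD or pneumonitis. Section 9.3.3 could fill the silence. This stands in part: a reader might infer that Table 5.1 bars restart after infection, and the text does not say so. But the respiratory row does not refer to Section 9.3.3, and a site following the table finds no instruction for a cause that the table itself names.

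**The exception clause is a route back.** It is, and it needs the same two parties as the stated route. With no criterion, though, it lets similar cases be decided differently.

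**The hold triggers differ.** One could read a precautionary hold on symptoms, followed by a mandatory hold once ILD is suspected. That works for cough or low-grade fever alone. It does not work for a radiological abnormality suggestive of ILD, which is suspected ILD.

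**Withdrawal at 21 days.** A reader might infer that a subject with infection must be withdrawn, because "If a subject requires a dosing delay longer than 21 days, the subject will be withdrawn from the study". That paragraph concerns interruptions due to DLTs, and the next concerns non-DLT events of Grade 3 and above. Neither names a Grade 2 event that is not a DLT at onset, so certain withdrawal is not supported.

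**Grades.** A reader might infer a conflict because the Table 5.1 row lists Grades 2 to 4 while confirmed Grade 1 ILD is a DLT. One passage manages dosing and the other defines DLTs; no opposing instruction for Grade 1 follows.

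**The model shift is not specific to ILD.** Correct: changing one subject's DLT status at n = 3 can do this whatever the cause. Under Section 3.2.1.2 the Sponsor also weighs clinical, PK and other data when choosing the dose.

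**Conclusion.** The inconsistency is real, in two parts. The hold is required in one passage and only recommended in the other. For restart, the passages apply different tests, which leaves confirmed infection or allergy without a stated rule in Table 5.1. The hold conflict does not depend on cycle or on DLT status.

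The effect on DLT counting is limited. It needs a Grade 2 event not attributed to disease, in the Dose Escalation DLT window, with treatment stopped on or before study day 23 and a Section 9.3.3 hold of at most 5 days within Cycle 1. Grade 3 or higher pulmonary toxicity is a DLT under either reading, and a Grade 1 event does not meet the missed-dose rule. It also assumes that a site takes Table 5.1's silence as no restart and that no exception is agreed. Within those limits, one subject's status can move the model recommendation from 800 mg to 400 mg, given the assumption about d. The documents do not support a wider claim that every infection during work-up changes DLT status.

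**What to change.** Reconcile the respiratory row of Table 5.1 with Section 9.3.3 so that both state the same hold (required or recommended, and on which trigger) and the same restart condition. Say explicitly which branch applies when an infectious or allergic cause is confirmed. Put the rule in one place and cross-refer from the other. The choice of rule belongs to the sponsor and its ILD committee; none is proposed here.

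The cost is amendment wording. The diagnostic work-up (Table 5.1) and ILD adjudication (Section 11.6.6) are already planned, and no new data are needed.
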